4.3.3 Investigation of subjects not returning to the study site

If a subject fails to return to the study site as scheduled, the principal investigator, subinvestigator, or clinical research coordinator will immediately investigate the reason for missed visits and the subsequent course.

5. Subject Consent

5.1 Timing of Informed Consent

Written informed consent must be obtained before the start of the screening period (before any protocol-specified testing, and before the start of washout for patients on nalfurafine hydrochloride).

5.2 Informed Consent Procedure

The principal investigator will prepare written information and consent forms with reference to the materials and information necessary to prepare these documents provided by the sponsor (e.g., examples of written information and informed consent forms), and obtain approval of the institutional review board (IRB).

The principal investigator or subinvestigator will select subjects who have sufficiently considered the objectives of the study from the ethical and scientific standpoints. Individuals incapable of giving consent will not be selected as subjects. When selecting an individual who may have an unreasonable disadvantage because he/she does not participate in the study, the principal investigator or subinvestigator must ensure that consent is given voluntarily by the subject.

Prior to the participation of each subject in the study, the principal investigator or subinvestigator will provide the subject with a thorough explanation using the written information. The principal investigator or subinvestigator will obtain voluntary written consent for study participation (informed consent form) from the subject after giving a chance to ask questions, answering to the questions sufficiently, and confirming that the subject has understood the information sufficiently. The informed consent form will be dated and signed (or affix name and seal) by the principal investigator or subinvestigator giving the explanation and dated and signed by the subject. Any clinical research coordinator giving a supplementary explanation will also date and sign (or affix name and seal) the informed consent form.

The principal investigator or subinvestigator will hand the written information and a copy of the informed consent form to the subject and retain the original informed consent form at the study site.

6. Study Drugs

6.1 Test Drug and Control Drug

6.1.1 Test drug

1) Code name: MR13A9

2) Nonproprietary name: Difelikefalin (INN)

- 3) Strength and dosage form:
 - MR13A9 0.025 mg/mL (injection): Each vial contains 1.3 mL of MR13A9 dissolved in 0.04 mol/L isotonic acetate buffer (pH 4.5) at a concentration of 0.025 mg/mL.
 - MR13A9 0.05 mg/mL (injection): Each vial contains 1.3 mL of MR13A9 dissolved in 0.04 mol/L isotonic acetate buffer (pH 4.5) at a concentration of 0.05 mg/mL.
 - MR13A9 0.1 mg/mL (injection): Each vial contains 1.3 mL of MR13A9 dissolved in 0.04 mol/L isotonic acetate buffer (pH 4.5) at a concentration of 0.1 mg/mL.
- 4) Storage conditions: Store at room temperature (1°C to 30°C)

6.1.2 Control drug

1) Strength and dosage form:

MR13A9 placebo (injection): Each vial contains 1.3 mL of 0.04 mol/L isotonic acetate buffer

(pH 4.5).

The MR13A9 placebo is indistinguishable from MR13A9 0.025, 0.05, or 0.1 mg/mL.

2) Storage conditions: Store at room temperature (1°C to 30°C)

6.1.3 Rationale for the control drug

With reference to the "Choice of Control Group and Related Issues in Clinical Trials" (MHLW PFSB/ELD Notification No. 136 dated February 27, 2001), a placebo has been selected as a control drug to control all potential influences on the actual or apparent course of the disease other than those arising from the pharmacologic action of the test drug (natural history of the disease, subject or investigator expectations, the effect of being in a trial, use of other therapy, and subjective elements of diagnosis or assessment).

6.2 Packaging of the Study Drugs

A total of 27 vials of MR13A9 0.025, 0.05, 0.1 mg/mL, or placebo (24 vials for 8 weeks + 3 spare vials) will be packed in 1 carton to prepare a carton per subject.

6.3 Labeling (Samples)

[figure not shown]

Figure 6.3-1 Vial Label

For investigational use MR13A9	Drug Number
Storage: Store at room temperature (1°C to 30°C) Serial No.: E8181	
Kissei Pharmaceutical Co., Ltd. Clinical Development [name] [contact]	Subject Identification Code

Figure 6.3-2 Carton label

6.4 Management of the Study Drugs

The study drug manager will manage and store the study drugs appropriately, as stipulated

separately in the written procedure.

7. Study Methods

7.1 Study Design

A placebo-controlled, multicenter, randomized, double-blind, parallel-group study

Screening period 2 weeks	Treatment period 8 weeks	Follow-up period 2 weeks
Placebo group		
	MR13A9 0.25-μg/kg group	
	MR13A9 0.5-µg/kg group	•
	MR13A9 1.0-μg/kg group	
	Restricted concomitant medications (anti-itch drug	gs)

Figure 7.1-1 Study Design

7.2 Doses and Dosing Method

7.2.1 Screening period

A 2-week period before entry into the treatment period is defined as the screening period, during which subjects will receive no study drug. Subjects will continuously use any restricted concomitant medications (e.g., anti-itch drugs) used at the start of the screening period.

7.2.2 Treatment period

In addition to the use of restricted concomitant medications (e.g., anti-itch drugs) used at the start of the screening period, the study drug will be injected into the venous line of the dialysis circuit at the end of each dialysis session for 8 weeks (3 times weekly, 24 times in total). The injected volume of the study drug will be determined based on the subject's dry weight on the day of dosing according to Table 7.2.2-1. If any dialysis circuit trouble precludes injection through the dialysis circuit, it will be permissible to administer the study drug as an intravenous injection. If a fourth dialysis session is extraordinarily required within the week, the study drug will be administered (up to 4 times weekly). If only the extracorporeal ultrafiltration method is used, the study drug will not be administered. Details are stipulated in a separate procedure.

Table 7.2.2-1 Doses

			MR13A	9 dose	
Dry weight	Injected volume	0.25 μg/kg	0.5 μg/kg	1.0 μg/kg	Placebo
		group	group	group	group
< 45.0 kg	0.35 mL	8.75 μg	17.5 μg	35.0 μg	0 μg
\geq 45.0 kg, $<$ 65.0 kg	0.50 mL	12.50 μg	25.0 μg	50.0 μg	0 μg
\geq 65.0 kg, $<$ 85.0 kg	0.70 mL	17.50 μg	35.0 μg	70.0 μg	0 μg
≥ 85.0 kg	0.85 mL	21.25 μg	42.5 μg	85.0 μg	0 μg

7.2.3 Follow-up period

A 2-week period after the end of the treatment period or the assessments at discontinuation in the treatment period is defined as the follow-up period, during which subjects will receive no study drug. Subjects will continuously use any restricted concomitant medications (e.g., anti-itch drugs) used at the start of the screening period.

7.2.4 Rationale for the doses

A dose-dependent improvement in itching was suggested in the Japanese phase II clinical study in hemodialysis patients with pruritus receiving MR13A9 0.25, 0.5, 1.0, or 1.5 μg/kg for 2 weeks (MR13A9-3). As for safety, all of these doses were tolerated, but the dose of 1.5 μg/kg was not considered suitable for a clinical dose, taking the occurrence of adverse drug reactions into account. It was thus determined that the efficacy and safety profiles of MR13A9 at 0.25, 0.5, and 1.0 μg/kg would be investigated in detail to determine the recommended clinical doses of MR13A9. For dose selection, body weight categories based on dry weight were established, taking the convenience of drug preparation into account.

In addition, an 8-week period that allows the efficacy evaluation of MR13A9 was established, provided that pruritus associated with hemodialysis requires prolonged treatment and that the improvement in itching was maintained after Week 2 in the non-Japanese phase II clinical study of MR13A9 that was administered for 8 weeks (CR845-CLIN2101).

7.3 Concomitant Treatments

7.3.1 Concomitant medications

Subjects may use any drug used to treat symptoms of chronic renal failure or drug used to treat complications at the start of the screening period without changing its dosage and administration whenever possible until the end of the follow-up period. It is permissible to change the dosage and administration of any concomitant medication for safety reasons such as the occurrence of adverse events.

7.3.2 Restricted concomitant medications

Between the start of the screening period and the end of the follow-up period, subjects may use the drugs listed below that have been used since before the screening period without changing their type or dosage and administration. In addition, do not newly use the drugs listed below:

- 1) Drugs indicated for the treatment of itching (prescription/nonprescription)
- 2) Moisturizing drugs (prescription/nonprescription)
- 3) In-hospital drugs formulated with either of the above
- 4) Antidepressants, antipsychotics, antiepileptics, hypnotics, anxiolytics, pregabalin, steroids (any route of administration)

Among the drugs listed in 1) to 3) above, topical use of any prescription/nonprescription drug for purposes other than the purpose of treating itching caused by chronic renal failure or any complication of chronic renal failure will not be restricted.

Use of any combination product that contains ingredients indicated for itching but is not indicated itself for itching will not be restricted.

7.3.3 Prohibited concomitant medications

Between the start of the screening period and the end of the follow-up period, use of the drugs listed in Table 7.3.3-1 will be prohibited.

Table 7.3.3-1 Prohibited concomitant medications

	Class	Common drugs
1)	Opioids	Nalfurafine hydrochloride, morphine, fentanyl, oxycodone,
		buprenorphine, pentazocine, codeine phosphate, dihydrocodeine
2)	Opioid antagonists	Naloxone hydrochloride, eptazocine hydrobromide, naldemedine
		tosylate
3)	Investigational product other than	Various kinds
	MR13A9	

7.3.4 Rationale for the prohibited concomitant medications

- 1), 2) To exclude their effects on the efficacy evaluation of MR13A9.
- 3) To exclude their effects when coadministered with MR13A9 on the safety evaluation of MR13A9.

7.3.5 Prohibited concomitant therapies

Between the start of the screening period and the end of the follow-up period, use of phototherapy to treat itching will be prohibited.

7.3.6 Rationale for the prohibited concomitant therapies

To exclude the effect of phototherapy on the efficacy evaluation of MR13A9.

7.4 Hemodialysis Conditions

Between the start of the screening period and the end of the follow-up period, the hemodialysis method (HD, off-line HDF, on-line HDF, or I-HDF) may not be changed. The dialysis conditions (frequency of dialysis per week, duration of dialysis, dialyzer, vascular access, dialysate flow rate, blood flow rate, and dialysate sodium concentration) may not be changed whenever possible, except for temporary changes with no changes in treatment strategies.

7.5 Randomization and Blinding

7.5.1 Treatment Assignment

The person responsible for treatment assignment will prepare a treatment assignment table to assign subjects to MR13A9 0.25, 0.5, or 1.0 μ g/kg, or placebo at a ratio of 1:1:1:1.

7.5.2 Preparation of emergency key codes

The person responsible for treatment assignment will prepare emergency key codes to allow immediate identification of the treatment assigned to each subject in emergencies.

7.5.3 Retention of the treatment assignment table and the emergency key codes

The person responsible for treatment assignment will seal the treatment assignment table and the emergency key codes so that blind-breaking can be detected, and retain them until

unblinding, as stipulated separately in the written procedure.

7.5.4 Subject registration

7.5.4.1 Primary subject registration

The principal investigator or subinvestigator will assess the eligibility of all subjects providing consent at the time of signing informed consent (see "4. Study Population"), enter necessary information in a primary subject registration form, and register the subjects by the next day.

The subject registration center will notify the principal investigator or subinvestigator about the acceptance or rejection of the primary subject registration for each subject.

The completed primary subject registration form and the primary subject registration confirmation form obtained from the subject registration center will be retained at the study site.

7.5.4.2 Secondary subject registration

The principal investigator or subinvestigator will assess the eligibility of each subject at the start of the screening period (see "4. Study Population"), enter necessary information in a secondary subject registration form, and register the subject by the next day.

The subject registration center will notify the principal investigator or subinvestigator about the acceptance or rejection of the secondary subject registration of each subject.

The completed secondary subject registration form and the secondary subject registration confirmation form obtained from the subject registration center will be retained at the study site.

For any subject eligible for primary registration but ineligible for secondary registration, the principal investigator or subinvestigator will notify the subject registration center about the reason for ineligibility.

7.5.4.3 Tertiary subject registration

The principal investigator or subinvestigator will assess the final eligibility of each subject at the start of the treatment period (see "4. Study Population"), enter necessary information in a tertiary subject registration form, and register the each subject promptly.

The subject registration center will notify the principal investigator or subinvestigator about the acceptance or rejection of the tertiary subject registration of each subject, and the drug number for the subject when the registration of the subject has been accepted. The principal investigator or subinvestigator will prescribe the study drug of the drug number notified by the subject registration center for the subject.

The completed tertiary subject registration form and the tertiary subject registration confirmation form obtained from the subject registration center will be retained at the study site.

For any subject eligible for secondary registration but ineligible for tertiary registration, the principal investigator or subinvestigator will notify the subject registration center about the reason for ineligibility.

7.5.4.4 Randomization of subjects

Based on the treatment assignment table, the subject registration center will randomly assign subjects eligible for tertiary registration to 4 treatment groups by a dynamic allocation method using 2 stratification factors: prior treatment with nalfurafine hydrochloride (for \geq 2 consecutive weeks in the year prior to the informed consent procedure) and specific signs or symptoms during the screening period (Appendix 2) confirmed before dialysis at Week 0.

7.5.5 Opening of emergency key codes

If the study drug assigned to a subject needs to be identified immediately in emergencies, the emergency key code for the drug number will be opened to identify the treatment, as instructed below:

- 1) In an emergency, the principal investigator or subinvestigator will promptly provide appropriate treatment for the subject, confirm his/her health condition, and report to the sponsor. If it is considered necessary to open the emergency key code for the subject to assure his/her safety, the principal investigator or subinvestigator will request the sponsor to open the emergency key code by telephone or other means.
- 2) If requested by the principal investigator or subinvestigator to open the emergency key code or if the sponsor considered necessary to open the emergency key code, the sponsor will open the emergency key code for the drug number, as stipulated separately in the procedure, and report the drug number to the principal investigator.
- 3) For the subject with the relevant drug number, the principal investigator will complete a case report form and a record of premature opening of a treatment assignment code and submit the documents to the sponsor.

7.5.6 Unblinding

The person responsible for treatment assignment will confirm that the blind has been maintained throughout the study period and then unblind the treatment assignment table.

7.5.7 Maintenance of the blind

To maintain the blind, the results of measurement of plasma drug concentrations will be kept and managed at the measurement organization until the unblinding of the treatment assignment table. Any information that can identify treatment groups or individual subjects will be reported to the sponsor and the study site after the unblinding of the treatment assignment table.

7.6 Sample Size

7.6.1 Sample size

This study will enroll 60 subjects for each MR13A9 dose group and the placebo group, 240 subjects in total.

7.6.2 Rationale for the sample size

In the non-Japanese phase II clinical study (CR845-CLIN2101), the change from baseline in NRS score at Week 8 (mean \pm standard deviation) was -3.9 ± 2.48 , -2.8 ± 2.24 , and -3.4 ± 2.34 in the MR13A9 0.5 μ g/kg, 1.0 μ g/kg, and combined (CR845 all doses) groups, respectively, versus -1.9 ± 2.29 in the placebo group. The difference in the change from

baseline in NRS score (least squares mean \pm standard error) in each of the MR13A9 0.5 μ g/kg, 1.0 μ g/kg, and combined groups versus the placebo group was -1.8 ± 0.50 , -0.8 ± 0.52 , and -1.3 ± 0.41 , respectively.

For the present study, the MR13A9 0.5 and 1.0 μ g/kg groups were assumed to have a similar change in NRS score at Week 8 of the treatment period to that observed in the MR13A9 combined group in the non-Japanese phase II clinical study. The MR13A9 0.25 μ g/kg group, for which no efficacy results were obtained, was assumed to have about half the change in NRS score assumed above. The mean difference in NRS score between each of the MR13A9 0.25, 0.5, and 1.0 μ g/kg groups and the placebo group was assumed to be -0.6, -1.3, and -1.3, respectively, with a common standard deviation of 2.5. When the dose-response relationship for the MR13A9 0.25, 0.5, and 1.0 μ g/kg groups was evaluated using the contrast patterns shown in "13.5.2.1.1 Primary analysis," with a two-sided significance level of 5% and a sample size of 60 subjects per group, a contrast pattern of 3, 1, -2, -2 (placebo, 0.25, 0.5, 1.0 μ g/kg) produced a statistical power of 91.7%. Statistical power is more than 80% when the MR13A9 0.5 or 1.0 μ g/kg group (60 subjects per groups) was compared with the placebo group.

With respect to the mean difference in NRS score at Week 2 of the treatment period, the MR13A9 0.5 and 1.0 μ g/kg groups were assumed to show a difference considered clinically meaningful versus the placebo group, and the MR13A9 0.25 μ g/kg group was assumed to show about half the difference above. The mean difference in NRS score versus the placebo group was assumed to be -0.4, -0.8, and -0.8 in the MR13A9 0.25, 0.5, and 1.0 μ g/kg groups, respectively, with a common standard deviation of 1.9. As with the evaluation of the doseresponse relationship at Week 8 of the treatment period, when the dose-response relationship for the MR13A9 0.25, 0.5, and 1.0 μ g/kg groups was evaluated using the contrast patterns, with a two-sided significance level of 5% and a sample size of 60 subjects per group, a contrast pattern of 3, 1, -2, -2 (placebo, 0.25, 0.5, 1.0 μ g/kg) produced a statistical power of 76.4%.

8. Subject Instructions and Management

The principal investigator or subinvestigator should sufficiently explain the significance and objectives of the study to subjects, and instruct and manage them especially for the following:

- 1) Confirm the absence of somnolence, dizziness, or similar symptoms after receiving the study drug and return home. Report any symptoms to the principal investigator or subinvestigator. Pay attention during hazardous machine operation and automobile driving during the treatment period. Avoid hazardous machine operation and automobile driving on the day of study treatment.
- 2) Maintain the symptom diary in subject every day. Record symptoms in the designated form and bring it at visit dates if any electronic diary system trouble makes the maintenance of the symptom diary impossible.
- 3) Take all prescribed drugs other than the study drug properly as instructed.
- 4) Be sure to visit the study site as scheduled. Inform the study site in advance if it is impossible to visit for some unavoidable reason. Visit the study site at the same time at every visit whenever possible.
- 5) Report the drug(s) used currently to the principal investigator or subinvestigator before participation in the study. Consult the principal investigator or subinvestigator before use about any new drug prescribed at other medical departments or hospitals or any over-the-

counter drug to be started. Report to the principal investigator or subinvestigator immediately if it was inevitable to use any drug without consultation.

6) Be sure to report in advance any visit to another department or hospital during the study period to the principal investigator or subinvestigator and report your participation in the study to the doctor at the department or hospital. If it is impossible to report in advance for unavoidable reasons such as an emergency visit, report your participation in the study to the doctor or pharmacist at the department or hospital and immediately report the visit to the department or hospital as well as prescribed drugs and other information to the principal investigator or subinvestigator.

- 7) Immediately inform the principal investigator or subinvestigator about any abnormalities in your body after undergoing tests at the end of the follow-up period (or at the time of discontinuation) or at the end of the follow-up investigation.
- 8) Women of childbearing potential must avoid intercourse during the study period or use appropriate contraceptive methods when having intercourse. Immediately inform the principal investigator or subinvestigator about any suspected pregnancy during the study period.
- 9) Men must avoid intercourse during the study period or use appropriate contraceptive methods when having intercourse. Immediately inform the principal investigator or subinvestigator about any suspected pregnancy of your partner between the start of study treatment and 12 weeks after the final dose.
- 10) Avoid disclosing any information related to this study, such as data used during the study, adverse events reported during the study, tests performed during the study, and personal remarks about administration of the study drug, on the Internet (e.g., Facebook, Twitter, blogs) or other information media (e.g., newspapers, magazines, advertisements).

9. Investigations, Observations, Tests, and Evaluations

The principal investigator and subinvestigator will perform investigations, observations, tests, and evaluations according to the study schedule (pages 49 and 50) and the respective procedures of investigations, observations, and tests.

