1.3.2.2 Efficacy and safety

In a Japanese phase II clinical study (MR13A9-3), 105 previously treated hemodialysis patients with pruritus received intravenous doses of MR13A9 0.25, 0.5, 1.0, or 1.5 µg/kg, or placebo 3 times weekly for 2 weeks. With respect to efficacy, the primary endpoint of change in VAS (i.e., change based on the larger VAS value either in the morning or the evening during the 7 days, the latter half of the treatment period) (mean \pm standard deviation) was 23.4 ± 20.0 mm, 28.0 ± 18.2 mm, 32.8 ± 25.4 mm, and 41.2 ± 22.8 mm in the 0.25, 0.5, 1.0, and 1.5 μ g/kg groups, respectively, versus 26.4 \pm 22.3 mm in the placebo group. These results suggested a dose-dependent improvement by treatment with MR13A9 at doses $\geq 0.5 \,\mu g/kg$. With respect to safety, the incidence of adverse drug reactions was 23.8% (5/21 subjects), 33.3% (7/21 subjects), 61.9% (13/21 subjects), 47.4% (9/19 subjects), and 82.6% (19/23 subjects) in the placebo, 0.25, 0.5, 1.0, and 1.5 µg/kg groups, respectively. Commonly reported adverse drug reactions (in ≥ 10% of subjects in any of the MR13A9 groups) included blood thyroid stimulating hormone decreased, dizziness, blood prolactin increased, nausea, feeling abnormal, and somnolence. The incidence of these adverse drug reactions was as follows: blood thyroid stimulating hormone decreased, 9.5% (2/21 subjects) in the 0.25 µg/kg group, 31.6% (6/19 subjects) in the 1.0 µg/kg group, and 30.4% (7/23 subjects) in the 1.5 μ g/kg group; dizziness, 4.8% (1/21 subjects) in the 0.25 μ g/kg group, 9.5% (2/21 subjects) in the $0.5 \mu g/kg$ group, 10.5% (2/19 subjects) in the $1.0 \mu g/kg$ group, and 17.4% (4/23 subjects) in the 1.5 µg/kg group; blood prolactin increased, 4.8% (1/21 subjects) in the $0.25 \mu g/kg$ group, 4.8% (1/21 subjects) in the $0.5 \mu g/kg$ group, 5.3% (1/19 subjects) in the $1.0 \,\mu g/kg$ group, and 17.4% (4/23 subjects) in the $1.5 \,\mu g/kg$ group; nausea, 4.8% (1/21 subjects) in the 0.25 μg/kg group and 17.4% (4/23 subjects) in the 1.5 μg/kg group; feeling abnormal, 4.8% (1/21 subjects) in the 0.5 µg/kg group and 17.4% (4/23 subjects) in the 1.5 µg/kg group; and somnolence, 4.8% (1/21 subjects) in the 0.25 µg/kg group, 4.8% (1/21 subjects) in the 0.5 µg/kg group, and 13.0% (3/23 subjects) in the 1.5 µg/kg group.

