4.3 Discontinuation of Individual Subjects

4.3.1 Discontinuation criteria (discontinuation of individual subjects)

- 1) Adverse event (The name of the adverse event should be recorded in the case report form):
 - It is necessary to withdraw the subject from the study because of the adverse event in the opinion of the principal investigator or subinvestigator
 - The subject does not want to continue the study due to the adverse event
- 2) Lack of efficacy (inadequate response):
 - Study continuation may cause an unacceptable risk to the subject because of the lack of efficacy of the study drug in the opinion of the principal investigator or subinvestigator
- 3) Voluntary request for study discontinuation by the subject (Discontinuation due to an adverse event is categorized as 1) above and discontinuation due to the lack of efficacy is

categorized as 2) above)

4) Significant protocol deviation during the study

- Any GCP violation is found
- After registration, the subject is found not meeting any of the inclusion criteria or meeting any of the exclusion criteria stipulated in the protocol
- Study continuation may cause injury to the subject because of the subject's protocol noncompliance in the opinion of the principal investigator or subinvestigator
- 5) Four consecutive missed doses of the study drug
- 6) Pregnancy
- 7) Discontinuation of the entire study
- 8) Discontinuation of the study at the study site
- 9) Lost to observation or follow-up
 - Study continuation becomes impossible because of failure to contact the subject
- 10) Any other cases where it is necessary to withdraw the subject from the study in the opinion of the principal investigator or subinvestigator (A detailed reason should be recorded in the case report form)

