13.1 Analysis Sets

When the full analysis set (FAS) and the per protocol set (PPS) are used as analysis sets, analyses will be performed based on the treatment group to which each subject has been assigned. When the safety set (SS) and the pharmacokinetic analysis set (PKS) are used as analysis sets, analyses will be performed based on the treatment group in which each subject has been treated actually.

- FAS: Population of subjects, excluding the following subjects: subjects with GCP violations, untreated subjects, discontinued subjects before entry to the treatment period, some of the ineligible subjects, and subjects with no available mean NRS score at baseline (Week 0)
- PPS: Population of subjects, excluding the following subjects from the FAS: ineligible subjects, discontinued subjects, deviators, and subjects with broken emergency key

codes, as the subjects to be excluded from the PPS

• SS: Population of subjects, excluding the following subjects: subjects with GCP violations, untreated subjects, and discontinued subjects before entry to the treatment period

• PKS: Population of subjects, excluding the following subjects from the SS subjects with no available plasma drug concentration data

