13.5.2.1 Analysis of the primary variable

13.5.2.1.1 Primary analysis

The primary analysis will be performed using a mixed-effects model for repeated measures (MMRM) with change from baseline in the mean NRS score at each time point as an objective variable; treatment group, time point, and treatment group-by-time point interaction as fixed effects; baseline mean NRS score and dynamic allocation factors, presence of prior treatment with nalfurafine hydrochloride, and presence of specific signs or symptoms to be confirmed in the screening period, as covariates; and subject as a random effect.

The analysis will include all available data obtained at each time point between Week 1 and Week 8 of the treatment period. Estimation will be performed using a restricted maximum likelihood method. An unstructured covariance structure will be used to estimate error variance. If the unstructured covariance structure fails to provide convergence, the structure that minimizes Akaike's Information Criterion (AIC), among the Toeplitz, first-order autoregressive, and compound symmetry structures, will be used. The degree of freedom will be adjusted with the Kenward-Roger method.

For the primary variable and the change from baseline in the mean NRS score at Week 2 of the treatment period, contrasts will be used to determine the dose-response relationship for the placebo group and the MR13A9 0.25, 0.5 and 1.0 μ g/kg groups. Contrast patterns (placebo, 0.25, 0.5, 1.0 μ g/kg) to be used will include (3, 1, -1, -3), (2, 2, -1, -3), (1, 1, 1, -1, -1), (3, -1, -1, -1), and (3, 1, -2, -2).

The adjusted mean change at each time point for each group and its two-sided 95% confidence interval will be presented. The adjusted mean between-difference in the change at each time point for the placebo group and the MR13A9 0.25, 0.5, and 1.0 μ g/kg groups and its two-sided 95% confidence interval as well as the p value will be presented.

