6.2 Handling of Dropouts or Missing Data

When there is a lack in the data used for analysis, all items other than the following items will be handled as missing values, and no imputation by statistical methods will be performed. Sensitivity analyses of the primary variable will use multiple imputation. The details are shown in "10.1.1.1.2 Sensitivity analysis."

If the number of days of observation during the evaluation period is less than 4 days as of the time of calculation of the mean NRS score and the mean itch score based on the Shiratori's severity criteria at each time point, the score at that time point will be handled as missing.

If the overall score or the subscores (symptoms score, emotions score, and functioning score) of the Skindex-16 or the responses to the questions used for calculation of the total score of 5-D Itch Scale are missing, the score will be handled as missing.

Any plasma drug concentration below the lower limit of quantification (BLQ) will be treated as 0.

Any BLQ values observed in laboratory test values will be handled as the values of the quantification limit.

In the calculation of geometric mean and geometric CV, values of 0 before log-transformation will be handled as missing values.

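### Does the stated pairwise power of more than 80% fail because 60 per group is both the enrolled and the analysed number?

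*Protocol*

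**What the plan says.** Protocol 7.6.1: "This study will enroll 60 subjects for each MR13A9 dose group and the placebo group, 240 subjects in total". Protocol 7.6.2 then works with 60 per group throughout. It assumes differences from placebo at Week 8 of -0.6, -1.3 and -1.3 for 0.25, 0.5 and 1.0 µg/kg, a common SD of 2.5 and a two-sided 5% level. It reports 91.7% power for the contrast (3, 1, -2, -2). For single doses it adds "Statistical power is more than 80% when the MR13A9 0.5 or 1.0" µg/kg group is set against placebo, with 60 per group in parentheses in the same sentence.

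Other sections foresee that some subjects will not contribute a Week 8 value:
- Protocol 4.3.1 lists individual discontinuation criteria, among them "Four consecutive missed doses of the study drug".
- Protocol 13.1 removes several kinds of subject from the FAS, including "some of the ineligible subjects, and subjects with no available mean NRS score at baseline (Week 0").
- SAP 6.2 sets a weekly mean to missing: "If the number of days of observation during the evaluation period is less than 4 days".

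The primary analysis is an MMRM with baseline NRS as a covariate. On incomplete subjects, Protocol 13.5.2.1.1 says: "The analysis will include all available data obtained at each time point between Week 1 and Week 8 of the treatment period".

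On the lowest dose, 7.6.2 describes the 0.25 µg/kg group as one "for which no efficacy results were obtained, was assumed to have about half the change in NRS score assumed above". Protocol 1.3.2.2 reports that in MR13A9-3 "105 previously treated hemodialysis patients with pruritus received intravenous doses of MR13A9 0.25, 0.5, 1.0, or 1.5" µg/kg or placebo, with a two-week VAS result for 0.25 µg/kg.

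**The concern.** A sample size section usually gives an evaluable number and then a larger number to enrol. Here the two are the same, although the plan has several routes by which a randomised subject can have no Week 8 value. The pairwise figure sits just above 80%, so losing one or two subjects per group takes it to or below 80% if only subjects observed at Week 8 are counted.

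This is the only power figure behind the single-dose comparisons. Those comparisons will be reported with confidence intervals and p-values in a study meant to inform dose selection. Someone reading a non-significant single-dose result might credit the design with more power than it had.

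A second point is one of wording. Saying that no efficacy results existed for 0.25 µg/kg seems to conflict with the MR13A9-3 result in 1.3.2.2.

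**Working it through.** **Inputs.** From Protocol 7.6.2: difference 1.3, SD 2.5, two-sided 5%, 60 per group; means relative to placebo 0, -0.6, -1.3, -1.3; contrast (3, 1, -2, -2). Loss of 5% or 10% is an assumption. The nearest figure in the documents is in 1.3.2.2: treatment discontinued or interrupted because of adverse events in 1/21, 2/21 and 1/19 subjects at 0.25, 0.5 and 1.0 µg/kg (4.8%, 9.5%, 5.3%) over two weeks. That count includes interruptions, so it is context and not a dropout rate.

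**Step 1: reproduce the contrast power.** Noncentrality = |Σcμ| / (SD × √(Σc²/n)).
- Σcμ = 1×(-0.6) + (-2)×(-1.3) + (-2)×(-1.3) = 4.6
- Σc² = 9 + 1 + 4 + 4 = 18
- Noncentrality at n = 60: 4.6 / (2.5 × √(18/60)) = 3.359

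With 4×60 - 4 = 236 degrees of freedom the power is 91.7%, the protocol's figure.

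**Step 2: reproduce the pairwise power.** Noncentrality = 1.3 / (2.5 × √(2/60)) = 1.3 / 0.4564 = 2.848. Power is 80.6% with 118 df, 81.0% with 236 df and 81.3% by the normal approximation. The stated figure is correct.

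**Step 3: lose subjects, counting only those observed at Week 8.**

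| n per group | Pairwise, df 2n-2 | Pairwise, df 4n-4 |
|---|---|---|
| 60 | 80.6% | 81.0% |
| 59 | 79.98% | 80.3% |
| 58 | 79.3% | 79.6% |
| 57 (5% loss) | 78.6% | 78.9% |
| 54 (10% loss) | 76.3% | 76.7% |

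The contrast power from Step 1 becomes 88.7% with 54 and 84.8% with 48, and is still 80.7% with 43.

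**Step 4: use the planned model.** Under an MMRM a subject who leaves early still adds information on Week 8 through the correlation between weeks. The assumptions are monotone dropout spread evenly over the weeks, with a constant correlation of 0.6 to 0.8 or AR(1) of 0.8 to 0.95. The variance of the Week 8 mean then gives an effective n, which goes into the Step 2 formula with 236 df.
- 5% loss: effective n 57.6 to 59.2, power 79.4% to 80.4%.
- 10% loss: effective n 55.2 to 58.3, power 77.7% to 79.8%.

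The low ends come from AR(1) 0.8. So 80% can hold with only 57 per group observed at Week 8.

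**Step 5: vary the SD.** Section 7.6.2 cites SDs of 2.24 (1.0 µg/kg), 2.29 (placebo), 2.34 (combined) and 2.48 (0.5 µg/kg). All lie below 2.5. Pairwise power with df 2n-2:

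| SD | n = 60 | n = 54 |
|---|---|---|
| 2.24 | 88.4% | 84.8% |
| 2.29 | 86.9% | 83.2% |
| 2.34 | 85.5% | 81.6% |
| 2.48 | 81.3% | 77.0% |

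**Step 6: baseline adjustment.** If 2.5 is an unadjusted SD and the correlation between baseline and change is 0.3 (assumed), the residual SD is 2.5 × √(1 - 0.09) = 2.385 and power with 54 is 80.1%. At an assumed 0.2 it is 78.0%.

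**Step 7: the 0.25 µg/kg wording.** The phrase in 7.6.2 follows a paragraph on Week 8 NRS in CR845-CLIN2101, which tested 0.5, 1.0 and 1.5 µg/kg but not 0.25. MR13A9-3 measured VAS over two weeks. Read in place, the phrase means that no Week 8 NRS result existed for that dose, and that is true.

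**The case for a change.** The strongest case for a change is that the MMRM does not rescue everyone. Subjects excluded from the FAS add nothing to it. The two-sample t-tests of each dose against placebo in SAP 10.1.2.1 use observed values without imputation, and the PPS drops discontinued subjects altogether, so the complete-case figures describe those analyses directly. The documents never say that 2.5 was chosen to absorb loss, and at 2.48 the reserve is small. Since single-dose estimates and p-values will be reported, an honest power statement costs only a sentence or two.

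All of that stands as description. What does not follow is a defect. The sentence in 7.6.2 carries its own condition of 60 per group, so a reader can see what it assumes. SAP 6.5.2 treats items other than the primary variable as references, and the PPS is supplementary. Exclusion for a missing baseline should be rare, because inclusion criterion 7 already requires at least 5 recorded NRS days before a subject enters treatment. Any replacement range for the power would rest on a loss rate and week-to-week correlations found in neither document, so it would be less secure than the figure it replaced.

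**Conclusion.** No change is needed. The pairwise power is correct as written at 60 per group. The true part of the concern is that no loss allowance is stated and that at exactly SD 2.5 there is almost no reserve. Under the planned model the cost is small: at most 0.6 points below 80% at an assumed 5% loss, and 0.2 to 2.3 points below at an assumed 10%, before any credit for baseline adjustment. At the cited SDs of 2.34 or lower there is no shortfall with 54 per group; at 2.48 there is. The contrast used to judge dose-response keeps 88.7% at 10% loss.

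A caveat in 7.6.2 would leave the number enrolled, every analysis and the reading of the primary result as they are, so nothing is gained. The phrase about 0.25 µg/kg is loose wording with one sensible reading, and the assumed halving of the effect does not depend on it. These conclusions rest on the assumed loss rates and, for the MMRM figures, on the assumed correlations.
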